10.3.3. Efficacy Analyses

10.3.3.1. Primary and Secondary Analyses

The following statistical tests [T1] (primary), [T2] (key secondary), and [T3] (key secondary) will be conducted sequentially ([T1], [T2], then [T3]) by a gatekeeping method. This guarantees that the overall type 1 error across the set of primary and key secondary hypothesis tests is 0.05. Other assessments will not be part of the gatekeeping procedure.

- [T1] Primary: placebo vs. lasmiditan 200 mg (pain free at 2 hours) will be based on logistic regression.
- [T2] Key secondary: dose response of placebo, lasmiditan 50 mg, 100 mg, and 200 mg (pain free at 2 hours) will be based on Cochran-Armitage trend test.
- [T3] Key secondary: placebo vs. lasmiditan 100 mg (pain relief at 2 hours) will be based on logistic regression.

The analysis population for [T1], [T2], and [T3] under the gatekeeping procedure is the mITT.

For [T1], [T2], or [T3], if an analysis ([T1] or [T2] or [T3]) is not statistically significant, then all subsequent analyses will be conducted but will be designated as exploratory rather than confirmatory.

For the [T1] analysis, the statistical test will be based on placebo vs. lasmiditan 200 mg using the logistic regression model that includes treatment (placebo, lasmiditan 50 mg, lasmiditan 100 mg, and lasmiditan 200 mg) and baseline usage of medications to reduce the migraine (Yes/No).

For the [T2] analysis, the Cochran-Armitage trend test will be based on placebo, lasmiditan 50 mg, lasmiditan 100 mg, and lasmiditan 200 mg. The trend parameter is (0, 50, 100, and 200).

For the [T3] analysis, the statistical test will be based on placebo vs. lasmiditan 100 mg using the logistic regression model that includes treatment (placebo, lasmiditan 50 mg, lasmiditan 100 mg, and lasmiditan 200 mg) and baseline usage of medications to reduce the migraine (Yes/No).

Other details, including additional covariates, if any, and the programming code for [T1], [T2], and [T3], and analysis methods for other secondary efficacy endpoints, will be specified in the SAP.

CCI
[REDACTED]

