5.2. Sample Size Determination

Approximately 1157 patients will be screened to achieve approximately 880 patients randomized, and approximately 624 patients with data for a migraine attack.

[Table LAIH. 5.1](#) illustrates the power calculation.

The power calculation is based on the results of the Study SPARTAN*. The primary endpoint (headache pain free at 2 hours postdose) results in SPARTAN were 21.3%, 28.6%, 31.4%, and 38.8% for placebo, lasmiditan 50 mg, lasmiditan 100 mg, and lasmiditan 200 mg, respectively, and the rates of headache pain relief at 2 hours postdose were 47.7%, 59.0%, 64.8%, and 65.0% for placebo, lasmiditan 50 mg, lasmiditan 100 mg, and lasmiditan 200 mg, respectively.

To ensure sufficient total statistical power for the primary and two key secondary analyses, the number of randomized patients will be set at 880. Considering 29% dropout rate, this sample size has 85.6% power. More specifically, the study will include:

- Number of screened patients = 1157.
- Number of randomized patients = 880 (= 1157*0.76, approximately 24% screen failure based on assumptions from LAIJ***), with [placebo:lasmiditan 50 mg:lasmiditan 100 mg:lasmiditan 200 mg] = 268:114:268:230 (7:3:7:6 ratio) for the attack.
- Number of patients who have a migraine attack = 624 (= 880*0.71, approximately 29% of patients would not dose to treat a migraine attack during the 8 week period based on SPARTAN/SAMURAI**), with [placebo:lasmiditan 50 mg:lasmiditan 100 mg:lasmiditan 200 mg] = 190:81:190:163 (7:3:7:6 ratio).

Note*: SPARTAN is the Study COL MIG-302/H8H-MC-LAHK.

Note**: SAMURAI is the Study COL MIG-301/H8H-MC-LAHJ.

Note***: LAIJ is the Study H8H-MC-LAIJ.

Note: The power is calculated based on simulation. In the simulation, the correlation between pain free and pain relief was assumed to be zero which would result in a conservative power.

Table LAIH. 5.1 Study Power Calculation

	Arm	N
Arm and number of patients	PLA	190
	LY50	81
	LY100	190
	LY200	163
	Total	624
Power	Primary [T1] : PLA vs LY200 = 93.6% (2 sided, alpha = 0.05) Key secondary [T2]: CA (PLA,LY50,LY100,LY200) = 94.9% (2 sided, alpha = 0.05) Key secondary [T3]: PLA vs LY100 = 91.2% (2 sided, alpha = 0.05) Total (primary and two key secondaries) = 85.6%	
Primary endpoint/Key secondary endpoints	[T1] and [T2]: Pain free at 2 hours postdose [T3]: Pain relief at 2 hours postdose	

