5.4. General Statistical Considerations

Statistical analysis of this study will be the responsibility of Lilly or its designee.

In general, we will use the following statistical methods unless otherwise specified. For detailed definitions of [T1] (primary objectives), [T2] and [T3] (2 key secondary objectives), see Section [5.6.1](#):

- For efficacy analyses based on proportion, the logistic regression used in [T1] will be applied. The model term includes treatment and baseline usage of preventive medications to reduce the frequency of migraine (Yes/No).
- When treatment group (PLA, LY50, LY100, LY200) is in a statistical model, it will be regarded as a categorical variable.
- For analysis based on continuous variable (change from baseline), if analysis of variance (ANOVA) is used then its covariate includes treatment and baseline usage of preventive medications to reduce the frequency of migraine (Yes/No). LSMeans will be used for estimation.
- For safety analyses and demographics, only descriptive statistics will be presented, and no statistical test will be conducted.
- Statistical tests will be conducted at a 2-sided significance level of 0.05. The 95% confidence interval will be presented if appropriate.
- No multiplicity adjustment for multiple tests (between the arms for the same efficacy objective, nor between the different objectives for the same arms) will be made except primary and two key secondary analyses ([T1], [T2], and [T3]).
- Analyses will be reported by 4 treatment groups (PLA, LY50, LY100, LY200) in general.
- Frequency tables such as those for AE or TEAEs will be sorted by LY_ALL, in decreasing frequency.
- For safety, 5 treatment groups (PLA, LY50, LY100, LY200, LY_ALL) will be displayed.
- For demographics, 6 treatment groups (PLA, LY50, LY100, LY200, LY_ALL, Overall) will be displayed. Here “Overall” means all combined arms (PLA + LY_ALL).
- For efficacy analyses based on proportions, odds ratio along with 95 % confidence interval will be calculated at 2 hours post-dose time point (each treatment vs. placebo).

- When Cochran-Mantel-Haenszel test is used for a multi-category response, baseline usage of preventive medications to reduce the frequency of migraine (Yes/No) is used for stratification (each treatment vs. placebo).

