5.6. Efficacy Analyses

5.6.1. Primary and Key Secondary Analysis

The following statistical tests [T1] (primary), [T2] (key secondary), and [T3] (key secondary) will be conducted sequentially ([T1], [T2], then [T3]) by a gatekeeping method. This guarantees that the overall type 1 error across the set of primary and key secondary hypothesis tests is 0.05. Other assessments will not be part of the gatekeeping procedure.

- [T1] Primary: placebo vs. lasmiditan 200 mg (pain free at 2 hours) will be based on Wald's test by logistic regression.
- [T2] Key secondary: dose response of placebo, lasmiditan 50 mg, 100 mg, and 200 mg (pain free at 2 hours) will be based on Cochran-Armitage trend test.
- [T3] Key secondary: placebo vs. lasmiditan 100 mg (pain relief at 2 hours) will be based on Wald's test by logistic regression.

The analysis population for [T1], [T2], and [T3] under the gatekeeping procedure is the mITT.

When testing sequentially ([T1], [T2], and [T3]), if one of them becomes statistically non-significant, then all subsequent analyses will be conducted but will be designated as exploratory rather than confirmatory. That means, if [T1] is not significant, then [T2] and [T3] are exploratory. If [T1] is significant but not [T2], then [T3] is exploratory.

Note that regardless of the test results in [T1], [T2], and [T3], the other secondary and exploratory analysis are not adjusted in multiplicity (Section [5.6.4](#)).

For the [T1] analysis, the statistical test will be based on placebo vs. lasmiditan 200 mg using the logistic regression model that includes treatment (placebo, lasmiditan 50 mg, lasmiditan 100 mg, and lasmiditan 200 mg) and baseline usage of preventive medications to reduce the frequency of migraine (Yes/No).

For the [T2] analysis, the Cochran-Armitage trend test will be based on placebo, lasmiditan 50 mg, lasmiditan 100 mg, and lasmiditan 200 mg. The trend parameter is 0, 50, 100, and 200. This is to estimate the dose-response relationship of lasmiditan (dose zero to 200mg).

For the [T3] analysis, the statistical test will be based on placebo vs. lasmiditan 100 mg using the logistic regression model that includes treatment (placebo, lasmiditan 50 mg, lasmiditan 100 mg, and lasmiditan 200 mg) and baseline usage of preventive medications to reduce the frequency of migraine (Yes/No).

A sample SAS code for logistic regression is;

```
proc logistic data = myData;  
  class TRT(param=ref ref="PL") baseMedUse;  

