5.6.2. Sensitivity Analysis

As sensitivity analysis for [T1] (primary), [T2], [T3] (key secondary), and MBS, following method will be conducted:

- The same analysis will be conducted based on ITT and PPS
- “non-responder” patients due to missing data (post baseline) will be excluded from (Reference Section [5.4.1](#)) mITT population

In addition, [T1] [T3] analysis will be conducted for patients who are in mITT and who have not vomited up to 2 hours. That is, eliminate patients who recorded vomiting at least once between 0 hour to 2 hours (inclusive), recorded in the eDiary.

In addition, as sensitivity analysis for [T1], separate subgroup models specified below will be fitted:

- [1] Previous triptan response (none + poor (0-1), good (2-3))
- [2] Baseline disability severity ('need complete bed rest', the others)
- [3] Baseline headache severity (moderate or severe)
- [4] Baseline associate symptom (with/without nausea)
- [5] Menstrual period (-2d before cycle to total 5 days)
- [6] Body weight (continuous variable)
- [7] Age (continuous variable)
- [8] Gender
- [9] Baseline migraine attacks (<=5 attacks per month, > 5 attacks per month)
- [10] Time of dose relative to onset of migraine (dosing time <= 1 hour, dosing time > 1 hour)
- [11] Duration of migraine history (<=median, > median)

The definition of [1] and [5] are the same as the one specified in Section [5.8](#).

The model term include treatment, baseline usage of preventive medications to reduce the frequency of migraine (Yes/No), subgroup, and treatment-by-subgroup interaction.

The response rate for each arm, along with 95% confidence interval, will be estimated based on LSMeans.

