Time to MBS-Free by Chosen Symptom Through 48 Hours Post-Dose: (Nausea, Phonophobia, Photophobia)

This is 3 separate subgroup analysis of “Time to MBS Free Through 48 Hours Post-Dose”. For example, the nausea analysis is based on those who chose “nausea” as the most bothersome symptom at baseline.

Disability

Disability is measured on a four-point scale: not at all (0); mild interference (1); marked interference (2); and need complete bed rest (3). Proportion of patients with score = 0 for each group at each post baseline time point is analyzed. Note that patients with 0 severity at baseline will be excluded from the analysis. In addition, frequency of each category will be summarized.

Incidence of Rescue or Recurrence Medication Use

The analysis is conducted for 3 time frames, depending on rescue or recurrence medication dose time after the treatment intake: [0h<=dose<2h], [2h<=dose<24h], and [24h<=dose<=48h].

A subject is defined to have used rescue or recurrence medication if at least one medication is used during the time frame. Definitions of rescue/recurrence medication are in PROTOCOL Section 7.2.1.1.

Incidence of Headache Recurrence Through 24/48 Hours Post-Dose

It is defined that patients with pain-free at 2 hours post-dose becomes mild (1) or more before or at 24/48 hours post dose. We consider missing data as “non-recurrence” at each time point.

PGI-C

PGI-C is measured on a seven-point scale from “very much better” to “very much worse.” Responder is defined as top two categories, "very much better" and "much better". In addition, frequency of each category will be summarized.

Sustained Pain Free at 24 hours and 48 hours

Sustained Pain-Free is defined as experiencing headache pain-free at two hours after the dose and at the indicated assessment time, having not used any rescue/recurrence medications after the dose up to the assessment timing.

Time to No Disability Through 24 Hours

Disability is measured on a four-point scale: not at all (0); mild interference (1); marked interference (2); and need complete bed rest (3).

No Disability timing is defined as the first time when severity becomes 0. Note that patients with 0 severity at baseline will be excluded from the analysis.

Summary of Symptom-Free at Assessment Times (Nausea, Phonophobia, Photophobia, Vomiting)

This is 4 separate analysis of the symptom.

Total Migraine Freedom

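### The confirmatory T1 and T3 logistic models leave out hour-0 headache severity; adding it is a cheap improvement worth roughly 0.1 to 1.3 points of power per test under assumed prognostic strengths

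*SAP*

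**What the plan says.** SAP 5.6.1 defines T1 (pain free at 2 hours, 200 mg against placebo): "For the [T1] analysis, the statistical test will be based on placebo vs. lasmiditan 200 mg using the logistic regression model that includes treatment" with four treatment levels, plus baseline preventive-medication use. T3 (pain relief at 2 hours, 100 mg against placebo) has the same terms, and the sample SAS code has treatment and medication use only. SAP 5.4 makes this the general rule for proportions: "The model term includes treatment and baseline usage of preventive medications to reduce the frequency of migraine (Yes/No"). Preventive use is also the only randomisation stratum (Protocol 7.2).

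The protocol left room for more. Section 10.3.3.1 says "Other details, including additional covariates, if any, and the programming code for [T1], [T2], and [T3"] will be given in the SAP. The SAP adds no covariate and gives no reason.

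Severity is collected and is used elsewhere:
- Protocol 9.1.1 has patients rate it before dosing on a four-point scale.
- SAP 5.3, condition [C2], admits only moderate or severe ratings to the mITT, so the value is complete and binary there.
- SAP 5.6.2 lists it for T1 as item ["3] Baseline headache severity (moderate or severe"), in a model that also has a treatment-by-severity interaction.
- SAP 5.8 has a severity subgroup (SUB6) and an aggressive-headache subgroup that depends partly on severity (SUB7).

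**The concern.** A baseline variable that predicts response usually raises the power of the logistic Wald test for treatment, and adjusting for it corrects chance imbalance between arms. Severity of the treated attack is a natural candidate. It cannot be handled by stratification: randomisation is at Visit 2, the attack follows within up to 8 weeks, and about 29% of randomised patients are expected never to dose. Balance is therefore expected on average but not enforced.

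None of the planned analyses supplies a main-effect, severity-adjusted treatment test for T1 or T3. The SAP 5.6.2 model covers T1 only and includes the interaction; the output named is response rates by arm. SUB6 and SUB7 give within-subgroup results and an interaction p-value. At stake is a small amount of power in two of the three gated tests, and some protection against an unlucky split of severe attacks.

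**Working it through.** **Inputs from the documents.** Pain-free rates: SAP 5.2, "results in SPARTAN were 21.3%, 28.6%, 31.4%, and 38.8% for placebo, lasmiditan 50 mg, lasmiditan 100 mg, and lasmiditan 200 mg". Pain-relief rates: "postdose were 47.7%, 59.0%, 64.8%, and 65.0% for placebo, lasmiditan 50 mg, lasmiditan 100 mg, and lasmiditan 200 mg, respectively". mITT sizes are 190:81:190:163. Level: "Statistical tests will be conducted at a 2-sided significance level of 0.05".

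**Inputs assumed.** The share of severe attacks (30%; 20% to 50% in the simulations) and the odds ratio of response for severe against moderate attacks. The documents give neither. The preventive-use term is left out of both models because no rates by use are given.

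**Step 1: the plan's own power.** For two arms,

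log OR = ln[p1/(1−p1)] − ln[p0/(1−p0)]; SE = √[1/(n0·p0(1−p0)) + 1/(n1·p1(1−p1))]; power ≈ Φ(log OR/SE − 1.96).

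- T1: log OR = −0.456 + 1.307 = 0.851 (OR 2.34). SE = √(1/31.85 + 1/38.71) = 0.239. z = 3.558; power 94.5%.
- T3: log OR = 0.610 + 0.092 = 0.702 (OR 2.02). SE = √(1/47.40 + 1/43.34) = 0.210. z = 3.342; power 91.6%.

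| | Stated | Large-sample Wald | Simulated Wald (T2: trend test) | Simulated, continuity-corrected (T1, T3) |
|---|---|---|---|---|
| T1 | 93.6% | 94.5% | 95.1% | 94.0% |
| T2 | 94.9% | – | 94.9% | 94.9% |
| T3 | 91.2% | 91.6% | 92.3% | 90.9% |
| All three | 85.6% | – | 87.0% | 84.9% |

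The simulations take pain free and pain relief as independent, as the SAP does. All results lie within 2 points of the stated figures, which therefore stand without any severity term.

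**Step 2: add severity.** Let s be the severe share and g the log odds ratio for severe against moderate. For each arm, solve (1−s)·expit(α) + s·expit(α+g) = p, so that the marginal rates stay at the planning values. The conditional treatment effect is α1 − α0. Its SE comes from inverting the information matrix of the four-arm model with the severity term.

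Example, T1, s = 30%, odds ratio 0.5: placebo response is 24.5% (moderate) and 13.9% (severe), and 0.7 × 24.5 + 0.3 × 13.9 = 21.3%. The conditional log OR is 0.867 with SE 0.2415, so z = 3.589 and power is 94.8%.

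| Severe vs moderate OR (30% severe) | T1 power (from 94.5%) | T1 gain, points | T1 conditional OR | T3 power (from 91.6%) | T3 gain, points |
|---|---|---|---|---|---|
| 0.7 | 94.6% | 0.1 | 2.35 | 91.8% | 0.2 |
| 0.5 | 94.8% | 0.3 | 2.38 | 92.2% | 0.6 |
| 0.35 | 95.2% | 0.7 | 2.42 | 93.0% | 1.3 |
| 0.25 (extreme) | 95.6% | 1.1 | 2.47 | 93.8% | 2.2 |

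As a sample-size equivalent (squared ratio of adjusted to unadjusted z), the first three rows are worth 0.5%, 1.7% and 3.7% for T1, and 0.6%, 2.4% and 5.5% for T3.

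**Step 3: simulation check.** With 20% to 50% severe, the T1 gain is −0.1 to +0.2 points at odds ratio 0.67, +0.2 to +0.4 at 0.5 and +0.5 to +0.9 at 0.33. The T3 gain is +0.1 to +0.3, +0.3 to +0.6 and +1.0 to +1.5. With 30% or 50% severe, the probability of passing all three tests rises by 0.3 to 0.4 points at 0.5 and by 1.2 to 1.4 at 0.33. At odds ratio 1 there is no gain.

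**Step 4: chance imbalance.** With 30% severe, the SD of the placebo-minus-200 mg difference in severe share is √[0.3 × 0.7 × (1/190 + 1/163)] = 4.9 points. A 2-SD imbalance (9.8 points) shifts the T1 log odds ratio by roughly 0.098 × |ln 0.5| = 0.07 to 0.098 × |ln 0.35| = 0.10, or 0.3 to 0.4 of its SE of 0.239.

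**The case against.** The other side is strong on several points.

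- **Design choice.** The model adjusts for the one stratification factor, and the protocol speaks of further covariates only if any. Adding none complies. This stands: no passage contradicts another.
- **Assumed benefit.** Both endpoints start from moderate or severe pain, and a reader might infer that severity must therefore be prognostic. The documents do not show this: both grades must reach the same end state, and no response rate by severity is given. This stands, which is why the gain is shown as a range that includes almost nothing.
- **Randomisation.** A reader might infer that randomisation cannot balance severity. It cannot be stratified, but it is balanced in expectation, and the test's alpha already allows for chance imbalance.
- **Adjustment has a cost.** The odds ratio becomes conditional on severity, in a study meant to bridge to Study 302/LAHK. The bridging criteria are redacted, so their dependence on the T1 and T3 models cannot be checked. In addition, SAP version 2 dropped the condition that the eDiary baseline be recorded before dosing, and its revision history says that patients who recorded it afterwards are now in the mITT. For them the covariate is not strictly pre-treatment. Both costs are real and shape the fix. The late ratings also feed [C2] and the endpoints, so the present model depends on them as well.
- **Already examined.** SAP 5.6.2, SUB6 and SUB7 do look at severity, so it is not ignored. They still do not give the adjusted overall test.

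**Conclusion.** The point holds as a cheap improvement. Hour-0 severity is available for every mITT patient, could not be stratified, and is absent from the confirmatory T1 and T3 models. With 30% severe and a severity odds ratio of 0.7 to 0.35, adding it is worth about 0.1 to 0.7 points of power for T1 and 0.2 to 1.3 for T3, plus correction of chance imbalance. Both inputs are assumptions; if severity is not prognostic there is no gain.

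Two stronger readings are not supported. A reader might infer that the study is underpowered or its power statement wrong: the stated figures do not rely on severity, and they reproduce within 2 points without it. A reader might also infer that power is lost for nothing: planned power already exceeds 91% for each test, T2 stands between T1 and T3 and is unchanged, and adjustment alters what the odds ratio measures.

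**What to change.** Before unblinding, in SAP 5.6.1:

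1. Add hour-0 headache severity (moderate/severe) as a main effect to the T1 and T3 logistic models.
2. Report the present model beside it as a supportive analysis, so that the odds ratio can be compared with the reference study on the same footing.
3. Repeat the adjusted T1 and T3 analyses without patients whose hour-0 rating was entered after dosing, and state how many there are per arm.

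The cost is one model term and a few extra table rows. It needs no new data, and protocol 10.3.3.1 already leaves additional covariates to the SAP. If the sponsor keeps the present primary model, the least to ask is a pre-specified severity-adjusted supportive analysis of both tests, or a sentence saying why there is none.

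Optional: the same idea applies to disability (ID 11 in SAP 5.6.3), where "Proportion of patients with score = 0 for each group at each post baseline time point is analyzed" without the hour-0 grade as a covariate. Patients at grade 0 are already excluded, SUB5 compares bed rest with the other grades, and the endpoint is not confirmatory, so this carries little weight.

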To achieve between-group comparability, the randomization will be stratified (yes or no) for current use of concomitant medication(s) that reduce the frequency of migraine episodes.

At Visit 2, patients will be provided with study drug to treat a single migraine attack. Site personnel will confirm that they have located the correct investigational product by entering a confirmation number found on the investigational product into the IWRS before patients leave the site at Visit 2.

7.2.1. *Selection and Timing of Doses*

The actual time of dose administration will be recorded in the patient's eDiary. Patients will be instructed to take 3 tablets as the treatment for a new migraine attack, along with the following instructions:

- The migraine must be at least of moderate or severe severity.
- The migraine must be treated within 4 hours of pain onset.
- No prior analgesic or acute migraine treatment within 24 hours of study drug administration has been taken to treat the current migraine attack.

7.2.1.1. *Rescue/Recurrence Medication*

Rescue medication will be permitted after completion of the 2 hour assessments if the migraine does not respond with study drug (patient is not headache pain free). If the migraine does not respond within 2 hours, a rescue dose of NSAIDs, acetaminophen, and/or antiemetic drugs may be taken after completion of the 2 hour assessments of the study drug dose. Triptans, ergots, opioids and barbiturates MUST NOT be used for rescue medication within 24 hours of study drug administration.

If the migraine responds within 2 hours (headache becomes pain free) but then recurs after 2 hours, a dose of NSAIDs, acetaminophen, and/or antiemetic drugs may be taken after completion

of the 2 hour assessments of the study drug dose. Triptans, ergots, opioids and barbiturates MUST NOT be used for recurrence medication within 24 hours of study drug administration.

The use of rescue and recurrence medication details will be recorded in the paper diary.

Figure LAIH.2 illustrates allowance period of these restricted rescue and recurrence medications.

[figure not shown]

Figure LAIH.2. Allowance of restricted rescue/ recurrence medications.

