- For Kaplan-Meier analysis, corresponding figures will be created. Quartiles and rates, along with 95% CIs, were estimated using the Kaplan-Meier method. Corresponding 95% CIs were estimated using the methods of Brookmeyer and Crowley, and Greenwood, respectively.
- When baseline usage of preventive medications to reduce the frequency of migraine (Yes/No) is included in a statistical model, it is based on CRF, not IWRs.
- Efficacy analyses are based on eDiary data, unless otherwise specified.
- Comorbid condition is based on Visit 1.
- When median is used for subgroup analysis (e.g. SUB4, body weight), the median is based on mITT population.

We will use the following analysis population rules unless otherwise specified (see population definitions in Section [5.3](#)):

- Protocol deviation summary will be based on all randomized and mITT/ITT.
- Demographics and Baseline characteristics will be based on mITT/ITT/safety population (SP).
- Efficacy analyses [T1], [T2], [T3], and MBS will be based on mITT/ITT/per-protocol set (PPS).
- Other efficacy and health outcome will be based on ITT.
- Safety analyses (e.g., AE, laboratory assessments/vital signs), medication, and treatment compliance/eDiary compliance will be based on SP.

When continuous variables, including change from baseline scores, is summarized using descriptive statistics, it will show n (number of subjects with available data), mean, median, standard deviation, minimum, and maximum.

Minimum and maximum values will be presented to the same precision as the raw data. Mean and median will be presented to one more decimal place than the raw data. Standard deviation will be presented to two more decimal places than the raw data. P-values will be presented to three decimal places.

Categorical variables will be summarized using counts and percentages. Unless otherwise specified, percentages will be calculated using the numbers of subjects in the summarized

population in each treatment group as denominators. Percentages will be presented with a precision of 1 digit after the decimal.

Observations collected prior to dosing will serve to determine a baseline measurement; the latest available measurement prior to dosing will be used as the baseline. For data collected by eDiary, the baseline values will be the Hour-0 assessment times identified in the eDiary.

SAS® software (version 9.2 or higher) will be used to perform most or all statistical analyses.

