5.6.3. Details of Efficacy Analyses

Table LAIH. 5.3 is the list of primary/ key secondary/ other secondary/ exploratory analysis with each analysis population, timeframe and analysis method.

Table LAIH. 5.3 Primary, Key Secondary, Other Secondary and Exploratory Efficacy Variables and Analysis Methods

ID	Type	efficacy variables	POP	Timeframe	Analysis
1	PRIM /2 ND	Headache Pain Free	mITT/ ITT/ PPS	up to 48h	LOGISTIC
2	2KEY	Pain Free Trend Test	mITT/ ITT/ PPS	2h	CA
3	2KEY /2ND	Headache Pain Relief	mITT/ ITT/ PPS	up to 48h	LOGISTIC
4	2 ND	MBS-Free	mITT/ ITT/ PPS	up to 48h	LOGISTIC
5	2 ND	Migraine Symptoms Present at Assessment Times (Nausea, Phonophobia, Photophobia, Vomiting)	ITT	up to 48h	LOGISTIC
6	OTH	MBS-Free by Chosen Symptom: (Nausea, Phonophobia, Photophobia)	ITT	up to 48h	LOGISTIC
7	2 ND	Time to Headache Pain Free Through 48 Hours Post-Dose	ITT	up to 48h	KM
8	2 ND	Time to Headache Pain Relief Through 48 Hours Post-Dose	ITT	up to 48h	KM
9	2 ND	Time to MBS-Free Through 48 Hours Post-Dose	ITT	up to 48h	KM
10	OTH	Time to MBS-Free by Chosen Symptom Through 48 Hours Post-Dose: (Nausea, Phonophobia, Photophobia)	ITT	up to 48h	KM
11	2 ND	Disability	ITT	0.5h/1h/2h/24h	LOGISTIC

12	OTH	Incidence of Rescue or Recurrence Medication Use	ITT	[0h-2h]/ [2h-24h]/ [24h-48h]	LOGISTIC
13	OTH	Incidence of Headache Recurrence Through 24/48 Hours Post-Dose	ITT	2h< recurrence <=24h 2h< recurrence <=48h	LOGISTIC
14	2 ND	PGI-C	ITT	2h/24h	LOGISTIC
15	2 ND	Sustained Pain Free at 24 Hours and 48 Hours	ITT	24h/48h	LOGISTIC
16	2 ND	Time to No Disability Through 24 Hours	ITT	up to 24h	KM
17	OTH	Summary of Symptom-Free at Assessment Times (Nausea, Phonophobia, Photophobia, Vomiting)	ITT	up to 48h	LOGISTIC
18	OTH	Total Migraine Freedom	ITT	up to 48h	LOGISTIC
19	OTH	Modified Sustained Pain Free at 24 Hours and 48 Hours	ITT	24h/48h	LOGISTIC
20	OTH	Time to Meaningful Pain Relief Through 48 Hours	ITT	up to 48h (including 6h/8h)	KM
21	OTH	Time to Pain Free Through 48 Hours	ITT	up to 48h (including 6h/8h)	KM
22	2 ND	Change from Baseline of EQ-5D-5L in Index Score	ITT	24h	ANOVA
23	2 ND	Change From Baseline of EQ-5D-5L in Visual Analog Scale	ITT	24h	ANOVA
24	2 ND	HRQoL Measured by MQoLQ in 5 Domains	ITT	24h	ANOVA
25	2 ND	Treatment Satisfaction	ITT	48h	CMH

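### T2 is the only confirmatory test that omits the preventive-use factor by which randomisation is stratified: a minor efficiency and consistency gap, not an error

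*SAP*

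**What the plan says.** Protocol 7.2 states that "the randomization will be stratified (yes or no) for current use of concomitant medication(s) that reduce the frequency of migraine episodes".

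SAP 5.6.1 tests T1 (200 mg, pain free at 2 hours) and T3 (100 mg, pain relief at 2 hours) with a "logistic regression model that includes treatment (placebo, lasmiditan 50 mg, lasmiditan 100 mg, and lasmiditan 200 mg) and baseline usage of preventive medications". SAP 5.4 puts the same yes/no factor in the other logistic models and the ANOVAs, and stratifies the Cochran-Mantel-Haenszel tests by it. On its source, SAP 5.4 says "it is based on CRF, not IWRs".

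For T2 (dose response, pain free at 2 hours), SAP 5.6.1 says that "the Cochran-Armitage trend test will be based on placebo, lasmiditan 50 mg, lasmiditan 100 mg, and lasmiditan 200 mg", with scores 0, 50, 100 and 200. Protocol 10.3.3.1 says the same. Neither names a stratum or covariate or gives a reason for leaving it out.

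For sensitivity, SAP 5.6.2 says "The same analysis will be conducted based on ITT and PPS", and adds a rerun without patients counted as non-responders because of missing data. In Table LAIH. 5.3 the entry "Pain Free Trend Test" has Cochran-Armitage as its only method.

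**The concern.** T1 and T2 use the same endpoint in the same mITT patients, but only T1 is adjusted for the factor that the allocation respects. If that factor predicts pain freedom and is balanced across arms, an unadjusted trend test overstates its own variance. It is then slightly conservative and gives up some power.

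T2 is also a gate: if T1 passes and T2 fails, T3 becomes exploratory. If T1 and T2 fell on opposite sides of 0.05, no prespecified adjusted trend test would show whether preventive use explains the difference. One added after unblinding would be post hoc.

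**Working it through.** **1. Is T2 alone?** In the unredacted text, the logistic models (including the subgroup and interaction models), the ANOVAs and the CMH tests all carry preventive use. The Kaplan-Meier analyses name no between-arm test. The T2 reruns change only the population or the handling of missing data. So T2 is the only confirmatory test, and the only visible inferential efficacy test, without the factor.

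**2. Reproduce the stated T2 power.** Inputs from SAP 5.2: n = 190, 81, 190, 163 (N = 624) and pain-free rates p = 0.213, 0.286, 0.314, 0.388. Scores d = 0, 50, 100, 200 are from SAP 5.6.1, and two-sided alpha 0.05 is from SAP 5.4.

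- Mean score d̄ = 55,650/624 = 89.18; mean rate p̄ = 186.54/624 = 0.2989.
- U = Σ n(d - d̄)p = 3,137.0.
- Null SD = √[p̄(1 - p̄) Σ n(d - d̄)²] = √(0.2989 × 0.7011 × 3,659,483) = 875.8.
- SD under the alternative = √[Σ n(d - d̄)² p(1 - p)] = 871.1.
- Power = Φ[(3,137.0 - 1.96 × 875.8)/871.1] = Φ(1.63) = 94.9%.

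This equals the stated 94.9%, which is therefore the power of the unstratified test. Simulation also gives 94.9%.

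**3. The stratified alternative (Mantel extension).** In stratum k, with K patients, x_i responders among n_i patients in arm i, and stratum means d̄ and p̄:

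- U_k = Σ (d_i - d̄) x_i
- V_k = [K/(K - 1)] p̄(1 - p̄) Σ n_i(d_i - d̄)²
- Z = ΣU_k/√ΣV_k, with one degree of freedom

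**4. Assumptions.** The documents give no share or effect for preventive use. Assumed: share 20%, 30% or 40%; odds ratio for pain freedom 1.0, 0.7, 0.5 or 0.3; overall arm rates held at the SAP values. For the planned design, 268/114/268/230 patients are randomised with strata balanced across arms, and each doses with probability 0.71. There were 400,000 simulated trials per scenario. Size was taken at a common rate of 21.3%.

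| Setting | Change in T2 power from stratifying (points) | Size, plain T2 | Size, stratified T2 |
|---|---|---|---|
| Planned design: 880 balanced, 29% not dosing | -0.04 to +0.69 | 4.64-5.05% | 4.96-5.03% |
| Exact balance among analysed patients | -0.01 to +0.53 | 4.51-5.07% | 4.96-5.05% |

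Under the planned design the gain is about +0.1 to +0.3 points at an odds ratio of 0.5, and the change is about -0.04 at worst at an odds ratio of 1.0. At a 40% share and an odds ratio of 0.3, power goes from 95.3% to 96.0%. There the stratified test alone is significant in 0.91% of trials and the plain test alone in 0.22%, a net 0.91 - 0.22 = 0.69 points. The Monte Carlo error of that difference is about √(0.0113/400,000) = 0.00017, or 0.02 points.

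**5. Cross-check.** A separate simulation with exact balance and a 35% share gives 95.0% to 95.1% (odds ratio 0.67), 95.0% to 95.3% (0.5) and 95.3% to 95.8% (0.33). Only an extreme case outside the assumed range, a 50% share with odds ratio 0.2, reaches +1.2 points (95.6% to 96.8%).

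**6. The chain of three tests.** Under exact balance, stratifying T2 changes the joint power of T1, T2 and T3 by 0.0 to +0.3 points. Joint power was not run for the planned design.

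**The case against.** The case for leaving T2 alone is substantial, and most of it stands.

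- **The test is valid and consistently specified.** A reader might infer that omitting a stratification factor inflates type I error, or that 94.9% is wrong. Neither follows: plain T2 stays at or slightly below 5% apart from simulation error, and the stated power is correct for the test planned. Nor does T2 break the SAP's own rule, because SAP 5.4 applies the logistic model to proportions only where nothing else is specified.
- **The gain is small and rests on assumed inputs.** A reader who ignores the stratified allocation could reach about +1.0 point of T2 power, but the trial does not use that design. The 29% who do not dose loosen the balance without removing it; the planned-design ceiling is about +0.7.
- **Related results are already planned.** SUB13 gives pain-free results at 2 hours within each preventive-use group, and the T1 model gives adjusted odds ratios for each dose against placebo. These show whether the factor matters. They do not supply an adjusted one-degree-of-freedom trend test.
- **The CRF value can differ from the IWRS stratum.** So the fix aligns T2 with T1 and T3, and not perfectly with the allocation. With 5% of values misclassified, run only for unbalanced allocation, the change was -0.07 to +0.87 points, against -0.04 to +1.03 without misclassification. Most of the gain survives.
- **The protocol names Cochran-Armitage.** Protocol 10.3.3.1 also leaves additional covariates and code for T1 to T3 to the SAP, so whether stratifying needs an amendment is a real question for the sponsor.

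**Conclusion.** The gap is real and minor. T2 omits a factor that the randomisation and the other two confirmatory tests use, and no visible analysis fills the gap. Error control and the stated power are unaffected.

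Under the planned design, stratifying is worth about 0 to +0.7 points of T2 power if 20-40% of patients use preventives and their odds ratio for pain freedom lies between 1.0 and 0.3. A moderate effect (0.5) gives about +0.1 to +0.3. With no effect the cost is about 0.04 points. The share and the odds ratio are assumptions. The case for acting is that the adjusted test costs almost nothing, makes T2 consistent with T1, and can be prespecified only before unblinding.

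**What to change.** Before unblinding, prespecify a stratified one-degree-of-freedom trend test: Mantel extension, scores 0/50/100/200, stratified by the same CRF-based preventive-use variable as T1. In SAS this is the CMH nonzero-correlation statistic with table scores.

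Two checks decide its role:

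1. Under Protocol 10.3.1, does the change alter a principal feature and so need an amendment?
2. Do the redacted bridging criteria still apply? The one visible line of SAP 5.9 refers to T1, T2 and T3, so they may depend on the T2 test.

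If no principal feature changes and the criteria still apply, use the stratified test as T2 and keep plain Cochran-Armitage as a sensitivity analysis. Otherwise keep plain Cochran-Armitage as the gate and add the stratified test as a prespecified T2 sensitivity analysis.

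The cost is SAP wording, one procedure call and the two checks, with no new data. If the stratified test becomes the gate and preventive use proves not prognostic, T2 loses about 0.04 points of power.
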